### 5.6.6 Other Safety Analyses

Karnofsky Performance Status (KPS) will be summarized by a shift table from baseline to worst postbaseline scale and by frequency counts for each category for each visit.

LVEF (%) obtained by echocardiography will be summarized. The lowest postbaseline value and change from baseline will be summarized with n, mean, SD, median, Q1, Q3, and range. A subject data listing will be provided.

In addition, LVEF quantitative values will be classified into the following 5 categories:

Hyperdynamic = LVEF greater than 70%

Normal = LVEF 50% to 70% (midpoint 60%)

Mild dysfunction = LVEF 40% to 49% (midpoint 45%)

Moderate dysfunction = LVEF 30% to 39% (midpoint 35%)

Severe dysfunction = LVEF less than 30%

A shift table from baseline to the worst postbaseline values will be generated.

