9.5.1.4.7 ECHOCARDIOGRAM OR MULTIPLE-GATED ACQUISITION SCAN

An echocardiogram or MUGA scan (using technetium-based tracer) will be performed to assess left ventricular ejection fraction (LVEF) as designated in the Schedule of Procedures/Assessments ([Table 7](#) and [Table 8](#)). MUGA scans or echocardiograms should be performed locally in accordance with the institution's standard practice. MUGA scans are the preferred modality; however, whichever modality is used for an individual subject at baseline should be repeated for all subsequent LVEF assessments for that subject. LVEFs as assessed by the institution will be entered onto the CRF. Investigator assessment will be based upon institutional reports.

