- h: Urine dipstick testing for subjects with proteinuria $\geq 2+$ should be performed on Day 15 (or more frequently as clinically indicated) until the results have been 1+ or negative for 2 consecutive treatment cycles). Urine dipstick testing should be performed preferably at the investigational site (but may be performed locally by the primary care physician or a local laboratory if the subject does not have to come for a visit to the site). If a new event of proteinuria $\geq 2+$ occurs, the subject must resume the Day 15 urine dipstick testing for evaluation of proteinuria until results are 1+ or negative for 2 consecutive treatment cycles. For subjects with proteinuria $\geq 2+$, see [Section 9.4.2.2, Management of Proteinuria](#), for further details.
 Note: During Cycle 3 and subsequent cycles, subjects may return to the clinic for the Day 15 visit if urine dipstick testing is required as specified above. The Day 15 visit is mandatory in Cycles 1 and 2.
- i: A comprehensive PE (including a neurological examination) will be performed at the Screening or Baseline Visit, on C1D15, on Day 1 of each subsequent cycle, and at the Off-Treatment Visit. A symptom-directed PE will be performed on C1D1 and at any time during the study as clinically indicated. Height will be measured at the Screening Visit only.
- j: Required if screening PE is performed >7 days prior to C1D1.

Table 7 Schedule of Procedures/Assessments in Study E7080-G000-307: Prerandomization and Randomization Phases

- k: Single 12-lead ECG. Subjects must be in the recumbent position for a period of 5 minutes prior to the ECG.
- l: MUGA scan or echocardiogram will be performed during the Screening Visit and during or within 1 week following the Off-Treatment Visit, or sooner if clinically indicated. Assessment should use the same methodology (MUGA or echocardiogram).

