9.7.1.8 Safety Analyses

Safety analyses will be based on the Safety Analysis Set. All safety analyses will be summarized by treatment arm. Adverse events and serious adverse events, laboratory test results, vital signs, and echocardiogram results (including LVEF) will be summarized. Safety data will be summarized using descriptive statistics. Categorical variables will be summarized by number and percentage. Continuous variables will be summarized using n (number of subjects with available data), mean, standard deviation, median, Q1, Q3, and range (minimum and maximum) unless otherwise specified.

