9.7.1.8.6 OTHER SAFETY ANALYSES

Descriptive statistics for LVEF assessed on echocardiogram or MUGA scans and changes from baseline will be presented by treatment arm. Percent reduction from baseline will also be summarized.

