## 5.6 Safety Analyses

All safety analyses will be performed on the Safety Analysis Set. Safety data, presented by treatment groups will be summarized on an “as treated” basis using descriptive statistics (eg, n, mean, standard deviation, median, Q1, Q3, minimum, and maximum for continuous variables; n [%] for categorical variables). Safety variables include treatment-emergent adverse events (TEAEs), clinical laboratory parameters, vital signs, 12-lead ECG and echocardiogram results including left ventricular ejection fraction (LVEF). Study Day 1 for all safety analyses is defined as the earliest date of the first dose of study drugs.

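### SAP 5.6.6 limits the LVEF summary to echocardiography, while the protocol plans it for echocardiogram or MUGA and prefers MUGA

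*SAP*

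**What the plan says.** **Protocol, collection.** Section 9.5.1.4.7 provides for LVEF by echocardiogram or MUGA, done locally in line with each institution's practice, and adds: "MUGA scans are the preferred modality; however, whichever modality is used for an individual subject at baseline should be repeated". The LVEF value is entered on the CRF whichever method is used. A footnote to Table 7 (Section 9.5.2) sets the timing: "MUGA scan or echocardiogram will be performed during the Screening Visit and during or within 1 week following the Off-Treatment Visit", or earlier on clinical grounds.

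**Protocol, analysis.** Section 9.7.1.8.6, the section specific to LVEF, covers both methods: "Descriptive statistics for LVEF assessed on echocardiogram or MUGA scans and changes from baseline will be presented by treatment arm". It then adds: "Percent reduction from baseline will also be summarized". The general paragraph in Section 9.7.1.8 is looser and names one method: "vital signs, and echocardiogram results (including LVEF) will be summarized".

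**SAP.** Section 5.6 lists among the safety variables "12-lead ECG and echocardiogram results including left ventricular ejection fraction (LVEF"). Section 5.6.6 opens its LVEF paragraph with: "LVEF (%) obtained by echocardiography will be summarized". It goes on to the lowest postbaseline value, change from baseline and a listing, and then separately to five LVEF categories with a shift table. Table 1 has a row labelled Echocardiography. MUGA is not named anywhere in the SAP. Section 7, on changes in the planned analyses, declares none.

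**The concern.** The SAP is the document that programmers follow. Its LVEF section names the data source, and the source named is not the one the protocol prefers. Because the protocol asks each subject to stay on the baseline method, a subject who starts on MUGA should have no echocardiographic LVEF at any visit. Restricting the summary to echocardiography would therefore remove that subject altogether, not just one visit.

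The choice of method follows local practice, so any omission would track sites and their imaging habits and would not be random. What is at stake is the completeness of a planned description of cardiac function in all three arms.

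**Working it through.** The SAP states no figure here that can be reproduced, so the check is a comparison of texts followed by an illustration of scale.

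**Step 1: the two LVEF-specific analysis sections.**

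| Item | Protocol 9.7.1.8.6 | SAP 5.6.6 |
|---|---|---|
| Source of LVEF | Echocardiogram or MUGA | Echocardiography |
| Change from baseline | Yes | Yes |
| Lowest postbaseline value | Not specified | Yes |
| Percent reduction from baseline | Yes | Not mentioned |
| Categories and shift table | Not specified | Yes, no method named |
| Listing | Not specified | Yes, no method named |

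The two disagree on the source, and SAP Section 7 does not declare the difference.

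**Step 2: which outputs the restriction reaches.**
- The first LVEF sentence of SAP 5.6.6 defines the variable as LVEF by echocardiography. The next sentence gives the statistics for that variable (lowest postbaseline value, change from baseline), so the restriction carries over to it.
- The five-category classification is introduced as an additional item and speaks of LVEF values in general. The restriction does not clearly reach it or the shift table.
- The listing sentence names no method. The opening of SAP Section 5 says that summarized variables are also listed, which ties listings to summaries but does not exclude anything.
- Table 1 assigns analysis sets to data categories and is stated not to be limiting. Its row label does not select data by imaging method.

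**Step 3: scale.** The documents do not give the share of subjects measured by MUGA. That "MUGA scans are the preferred modality" does not show how often it is used. Taking the share *p* as an assumption, and the planned figure of about 350 subjects per arm:

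subjects per arm outside the summary = *p* × 350

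- *p* = 10%: 0.10 × 350 = 35
- *p* = 50%: 0.50 × 350 = 175
- *p* = 90%: 0.90 × 350 = 315

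These are upper figures for each *p*. The lowest postbaseline value and the change from baseline also need a postbaseline scan, which is scheduled only around the Off-Treatment Visit. Subjects without one are absent from those summaries whatever the method.

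**The case against.** The strongest answer is that echocardiography is shorthand here for the LVEF assessment. The protocol's own overview in 9.7.1.8, and the matching Synopsis text, name only echocardiogram results, yet 9.7.1.8.6 in the same protocol covers both methods. SAP 5.6 repeats nearly the same phrase. Nothing in the SAP says that MUGA values are excluded, and Section 7 declares no departure from the protocol. This is a fair reading and may well be what was meant. It does not remove the point: the protocol's LVEF-specific section corrects its loose overview, whereas the SAP's LVEF-specific section adds a qualifier about how the value was obtained, and that reads as a selection rule.

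A reader might also infer that cardiac safety data would be dropped from the trial, or that MUGA subjects would leave the shift table and listing too. The documents do not support either. LVEF by either method stays on the CRF. The shift-table and listing sentences name no method. Unfavorable cardiac findings remain reportable as adverse events under protocol 9.5.1.4.1, irrespective of imaging method. Nor can a particular loss, such as half the subjects, be claimed, because the MUGA share is unknown.

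**Conclusion.** The mismatch is certain and its practical effect is not. As written, SAP 5.6.6 conflicts with protocol 9.7.1.8.6 and, if followed literally, leaves subjects measured by MUGA out of the descriptive summaries of lowest postbaseline LVEF and change from baseline.

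The size cannot be determined from the documents. It runs from no subjects, if the wording is shorthand or no site uses MUGA, to most of them, if MUGA predominates and the sentence is applied literally. The conclusion rests on that literal reading and on subjects keeping their baseline method, as the protocol asks.

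The effect is confined to descriptive safety reporting. No hypothesis test, efficacy endpoint or error rate is touched. The point is minor but worth correcting, since the correction has no drawback.

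**What to change.** - In SAP 5.6.6, reword the source to *LVEF (%) obtained by MUGA scan or echocardiography*.
- State that change from baseline is computed within the subject's baseline method. The protocol already asks sites to keep the method; the sentence tells the programmer what to do if a subject was switched.
- Show the method in the subject listing.
- Align the wording in SAP 5.6 and relabel the Table 1 row, for example *LVEF (MUGA/echocardiography)*.
- In the same edit, either restore the protocol's percent reduction from baseline, which SAP 5.6.6 does not mention, or declare its omission in Section 7.

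The cost is SAP wording and small changes to table and listing specifications. No new data, visits or subjects are needed. If the echocardiography-only summary was intended, the alternative is to say so in Section 7 and give the reason.

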## 5.7 Other Analyses

A detailed analysis plan for health-related quality of life will be provided in a separate document. Protocol deviations and adverse events associated with COVID-19 (coronavirus disease 2019) will be presented.

## 5.8 Exploratory Analyses

Exploratory analyses may be conducted as appropriate. Any exploratory analyses that are performed will be appropriately titled and labeled as exploratory and will be clearly distinguished from planned analyses when results are reported in the clinical study report.

## 5.9 Extension Phase Analyses

A separate SAP will be written for Extension Phase analyses, if needed.

## 6 INTERIM ANALYSES

Interim analyses of PFS, OS, and ORR are planned in this study. The interim analyses will be conducted by an independent statistical group (eg, a CRO) that has no other responsibilities for the study. The timing of each analysis are summarized in [Table 6](#). Type I error control for the efficacy analyses as well as efficacy boundaries are described in [Section 5.3.3](#).

The safety monitoring and interim analyses for PFS and OS will be conducted by the independent Data Monitoring Committee (DMC). The recommendation as to whether to stop the trial will be reached by the DMC based on their review of safety data and efficacy data with treatment information. The function and membership of the DMC will be described in the DMC Charter. The external DMC will conduct regular safety monitoring. The timing of the safety monitoring will be specified in the DMC Charter.

**Table 6 Summary of Interim and Final Efficacy Analyses**

No.	Analysis	Endpoint(s)	Timing	Estimated Time after First Subject Randomized
1	Interim analysis of ORR and DOR (the first 88 subjects from Arm B)	ORR DOR	Median follow-up of 12 months and a minimum DOR follow-up of 6 months	~28 months
2	Interim analysis of PFS, Interim analysis of OS	PFS OS ORR*	Trigger: approximately 4 months after the last subject randomized and approximately 310 (80% IF) PFS events observed in Arms B and C  (estimated to have ~140 (45% IF) deaths observed for each comparison)	~38 months
3	Final analysis of PFS, Interim analysis of OS	PFS OS	Trigger: ~ 388 PFS events observed for each comparison (estimated to have 182 (60% IF) deaths observed for each comparison)	~45 months
4	Interim analysis of OS	OS	Trigger: ~243 (80% IF) deaths observed for each comparison	~57 months
5	Final analysis of OS	OS	Trigger: ~304 deaths observed for each comparison	~69 months

DOR = duration of response; ORR = objective response rate; OS = overall survival; PFS = progression-free survival; IF=information fraction.

\*: The p-value for hypothesis testing of ORR will be based on the ORR data at the analysis No 2.

## 7 CHANGES IN THE PLANNED ANALYSES

Not applied.

## 8 DEFINITIONS AND CONVENTIONS FOR DATA HANDLING

### 8.1 EFFICACY DATA HANDLING

#### 8.1.1 Visit Windows for Efficacy Analysis

Tumor assessments were to be performed every eight weeks during the Randomization Phase and according to the local standard of care in the Extension Phase (or sooner if clinically indicated) until documentation of disease progression. Time window for radiologic assessment is  $\pm 5$  days.

For definitions, derived variables and data sets, please refer to the data set specifications for more details. The following points should be noted:

- Confirmed CR/PR and unconfirmed CR/PR will be derived.

- Early death will refer to the death which occurred within 121 days after randomization.

$$\text{Date of death} - \text{Date of randomization} \leq 121 \text{ days}$$

### 8.1.2 Missing/Partial Dates

Refer to programming specifications for details to handle any missing or partial dates.

## 8.2 Safety and Disease History Data Handling

### 8.2.1 Visit Windows for Safety Analyses

Visit windows will be defined to be upper and lower bounds of one day of the scheduled visit, following the protocol, which states that efforts should be made to conduct laboratory assessments and administer treatment on the day scheduled ( $\pm 1$  day). In the calculation of descriptive statistics for laboratory values and vital signs, if a visit has multiple observations, the observation closest in date and time to the target visit day will be used in the analysis. If two or more observations have the same distance to the target visit day, the one that has the highest CTCAE grade or is furthest away from the normal range will be used.

The purpose of this windowing is to provide a single record per subject per visit for the calculation of descriptive statistics per scheduled visit, and change from baseline per visit. Other safety analyses (e.g., worst grade laboratory results) will include all observations.

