9.4.8 Selection and Timing of Dose for Each Subject

Lenvatinib capsules are to be taken with water orally once a day at approximately the same time each day for 21 days in each cycle from Cycle 1 onward.

If a subject misses a dose of lenvatinib or everolimus, it may be taken within 12 hours following the usual time of the dose. If more than 12 hours have elapsed from the time of the usual daily dose, lenvatinib and/or everolimus should be taken the next day at the usual time. In the event a subject vomits after study drug administration, the subject should not take another dose until the next scheduled dose.

For subjects receiving combination lenvatinib plus everolimus, the 2 drugs should be administered in immediate succession.

For subjects receiving combination lenvatinib plus pembrolizumab, pembrolizumab will be administered at a dose of 200 mg as a 30-minute IV infusion, Q3W (infusion durations of 25 minutes to 40 minutes are acceptable) on Day 1 of each 21-day cycle. The Pharmacy Manual contains specific instructions for the preparation of the pembrolizumab infusion and its administration. Subjects should maintain a normal diet unless modifications are required to manage an AE such as diarrhea, nausea or vomiting. Study treatment of pembrolizumab may be administered up to 3 days before or after the scheduled Day 1 of each cycle due to administrative reasons. On Day 1 (D1) of Cycles 1 and 2, lenvatinib will be administered approximately within 4 hours after completion of pembrolizumab administration.

Sunitinib will be administered orally in accordance with the prescribing information.

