9.5.2 Schedule of Procedures/Assessments

[Table 7](#) (Prerandomization and Randomization Phase) and [Table 8](#) (Extension Phase) present the schedules of procedures/assessments for the study.

Table 7 Schedule of Procedures/Assessments in Study E7080-G000-307: Prerandomization and Randomization Phases

Phase	Prerandomization		Randomization All Cycles are 21 Days in Duration								
	Screening ^a	Baseline ^a	Treatment Period							Follow-up Period	
Visit	1	2	3	4	5	6	7	8, 9, etc.		98	99
Day	-28 to -3	-3 to -1	Cycle 1 ^b			Cycle 2 ^c		Cycle 3 – Last ^c		Off-Treatment Visit	
			1	8	15	1	15	1	15		
Procedures/Assessments											
Informed consent	X										
Inclusion/exclusion criteria	X	X									
Randomization ^d			X								
Demographic data	X										
KPS ^e	X	X				X		X		X	
NYHA ^e	X										
RCC AJCC staging (at the time of initial diagnosis of RCC) ^e	X										
Medical/surgical history	X	X									
Phone contact or visit ^f				X							
Vital signs and weight ^g	X	X	X		X	X	X	X	X	X	
Physical Examination ⁱ	X	X ^j			X	X		X		X	
12-Lead ECG ^k	X		X			X		X		X	
MUGA scan or echocardiogram ^l	X									X	
Hematology and clinical chemistry ^m	X	X			X	X	X	X		X	

Table 7 Schedule of Procedures/Assessments in Study E7080-G000-307: Prerandomization and Randomization Phases

Phase	Prerandomization		Randomization All Cycles are 21 Days in Duration								
	Screening ^a	Baseline ^a	Treatment Period							Follow-up Period	
Visit	1	2	3	4	5	6	7	8, 9, etc.		98	99
Day	-28 to -3	-3 to -1	Cycle 1 ^b			Cycle 2 ^c		Cycle 3 – Last ^c		Off-Treatment Visit	
			1	8	15	1	15	1	15		
Procedures/Assessments											
Urine dipstick testing ^h	X	X			X	X	X	X	X	X	
Pregnancy test ⁿ	X	X				X		X		X	X
HRQoL ^o		X				X		X		X	
PK blood sample ^{p,q}			X		X	X		X			
Pembrolizumab PK blood samples ^r			X			X		X		X	
Biomarker (serum) sample ^s			X		X	X		X		X	
Biomarker (plasma) sample ^s			X		X	X		X		X	
Biomarker (whole blood) sample ^s			X		X	X		X		X	
Tumor assessments (CT/MRI) ^t	X		Performed every 8 weeks (from the date of randomization), or sooner if clinically indicated, until IIR confirmation of disease progression.							X ^{t,u}	X ^t
Bone Scan ^v	X		Performed every 24 weeks and as clinically indicated.								X ^v
Brain scan ^w	X		X							X ^{u,w}	X ^w
Archival tumor block or slides ^x			X								
Survival and PFS2 ^y											X

Table 7 Schedule of Procedures/Assessments in Study E7080-G000-307: Prerandomization and Randomization Phases

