Phase	Prerandomization		Randomization All Cycles are 21 Days in Duration								
	Screening ^a	Baseline ^a	Treatment Period							Follow-up Period	
Visit	1	2	3	4	5	6	7	8, 9, etc.		98	99
Day	-28 to -3	-3 to -1	Cycle 1 ^b			Cycle 2 ^c		Cycle 3 – Last ^c		Off-Treatment Visit	
			1	8	15	1	15	1	15		
Procedures/Assessments											
Blood sample for PG analysis ^z			X								
Study drug treatment			21 day cycles of lenvatinib daily plus everolimus daily or 21 day cycle of lenvatinib daily plus pembrolizumab IV every 21 days or sunitinib daily for 4 weeks plus 2 weeks off, depending on randomization arm								
Concomitant medications ^{aa}	Throughout										
AEs/SAEs ^{bb}	Throughout										

A AE = adverse event; AJCC = American Joint Committee on Cancer; BP = blood pressure; CR = complete response; CT = computed tomography; BW = body weight; C = cycle; D = day; ECG = electrocardiogram; eCRF = electronic case report form; ¹⁸F-NaF = ¹⁸F-sodium fluoride; HR = heart rate; HRQoL = Health-related Quality of Life; ICF = informed consent form; ICL = imaging core laboratory; IV = intravenous; KPS = Karnofsky performance status; MRI = magnetic resonance imaging; MUGA = multiple-gated acquisition; NAb = neutralizing antibody(ies); NYHA = New York Heart Association; PE = physical examination; PFS2 = progression-free survival after start of next-line therapy; PG = pharmacogenomics; PK = pharmacokinetics; RCC = renal cell carcinoma; RR = respiration rate; SAE = serious AE.

Table 7 Schedule of Procedures/Assessments in Study E7080-G000-307: Prerandomization and Randomization Phases

- a: Subjects must be screened within 28 days prior to randomization. The screening assessment can serve as the baseline assessment, if performed within 72 hours before randomization. The baseline assessments can be performed within 72 hours or prior to randomization on C1D1. An ICF should be signed by the subject before any screening procedures are performed. Informed consent may be obtained up to 4 weeks prior to C1D1.
- b: Efforts should be made to conduct study visits on the day scheduled (± 1 day). Clinical laboratory assessments may be conducted anytime within 72 hours prior to the scheduled visit, unless otherwise specified in the Schedule of Procedures/Assessments.

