- c: Efforts should be made to conduct study visits on the day scheduled (± 3 days). Clinical laboratory assessments may be conducted anytime within 72 hours prior to the scheduled visit, unless otherwise specified in the Schedule of Procedures/Assessments.
- d: Subjects will be randomized on C1D1 (-1 day) after confirmation of eligibility at the Baseline Visit. All procedures and assessments on C1D1 should be performed after randomization.
- e: See protocol appendices for KPS assessments, NYHA Cardiac Disease Classification, AJCC Staging.
- f: Telephone contact or visit on C1D8 will assess subjects for development of early toxicity. An unscheduled visit can occur prior to C1D15 if deemed necessary by the investigator.
- g: Assessments will include vital signs (resting BP [including date and time of measurement for the first 6 treatment cycles], HR, RR, and body temperature) and BW. Only 1 BP measurement is needed for subjects with systolic BP <140 mmHg and diastolic BP <90 mmHg. If the subject's initial BP measurement is elevated (ie, systolic BP ≥ 140 mmHg or diastolic BP ≥ 90 mmHg), the BP measurement should be repeated at least 5 minutes later. The mean value of 2 measurements at least 5 minutes apart is defined as 1 BP assessment. If the BP assessment (ie, the mean of the 2 BP measurements obtained at least 5 minutes apart) is elevated (ie, systolic BP ≥ 140 mmHg or diastolic BP ≥ 90 mmHg), a confirmatory assessment should be obtained at least 30 minutes later by performing 2 measurements (at least 5 minutes apart) to yield a mean value. Subjects with systolic BP ≥ 160 mmHg or diastolic BP ≥ 100 mmHg must have their BP monitored on Day 15 or more frequently as clinically indicated) until their systolic BP has been ≤ 150 mmHg and diastolic BP has been ≤ 95 mmHg for 2 consecutive treatment cycles. If a repeat event of systolic BP ≥ 160 mmHg or diastolic BP ≥ 100 mmHg occurs, the subject must resume the Day 15 evaluation until systolic BP has been ≤ 150 mmHg and diastolic BP has been ≤ 95 mmHg for 2 consecutive treatment cycles. A diary will be provided to the subject to capture the blood pressure evaluations between study visits. See [Section 9.4.2.1, Management of Hypertension](#), for further details.
 Note: During Cycle 3 and subsequent cycles, subjects may return to the clinic for the Day 15 visit if BP monitoring is required as specified above. The Day 15 visit is mandatory in Cycles 1 and 2.

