### 5.6.3 Laboratory Values

Laboratory results will be summarized using Système International (SI) units, as appropriate. Laboratory values that are non-missing and reported as ‘below the detectable limit’ of an assay will be replaced by half the detectable limit in the summary tables. On treatment laboratory tests will be defined as laboratory tests conducted from the start of treatment to no more than 30 days after the last dose of study treatment. Central laboratory test results will be primary data source for laboratory analyses. Only when the central laboratory tests results are missing, the local laboratory test results will be used as substitute. Other laboratory parameters collected for some individual subjects will be presented in listing only. Box and Whisker plots will also be generated for individual laboratory parameters and change from baseline by visit for all visits with at least 10% of subjects in all treatment arms.

For all quantitative parameters listed in protocol Section 9.5.1.4 Safety Assessments (Laboratory Measurements), the actual value and the change from baseline to each postbaseline visit and to the end of treatment (defined as the last on-treatment value) will be summarized by visit and treatment group using descriptive statistics. Qualitative parameters listed in protocol Section 9.5.1.4 will be summarized using frequencies (number and percentage of subjects), and changes from baseline to each postbaseline visit and to end of treatment will be reported using shift tables. Percentages will be based on the number of subjects with both nonmissing baseline and relevant postbaseline results.

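### SAP 8.2.1 applies a ±1-day window to all safety visits and attributes it to the protocol, but Protocol Table 7 gives ±1 day for Cycle 1 visits only

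*SAP*

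**What the plan says.** SAP Section 8.2.1 defines the windows for safety analyses: "Visit windows will be defined to be upper and lower bounds of one day of the scheduled visit". It draws no distinction by cycle. It gives its source as a protocol statement that "efforts should be made to conduct laboratory assessments and administer treatment on the day scheduled", with a tolerance of one day either way. The stated aim is to have one value per subject at each visit for the descriptive and change-from-baseline tables. Where a visit has several laboratory or vital-sign values, the closest to the target day is used, and a tie rule follows. Other safety analyses use every observation.

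Protocol Section 9.5.2, Table 7, has two visit windows:

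- Footnote b, attached to the Cycle 1 column: "Efforts should be made to conduct study visits on the day scheduled (± 1 day".
- Footnote c, attached to the Cycle 2 and Cycle 3 to last columns: "Efforts should be made to conduct study visits on the day scheduled (± 3 days".

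Both footnotes add, unless otherwise specified: "Clinical laboratory assessments may be conducted anytime within 72 hours prior to the scheduled visit". Footnote m, on the hematology and chemistry row, repeats the 72-hour allowance. On treatment timing, Protocol Section 9.4.8 says: "Study treatment of pembrolizumab may be administered up to 3 days before or after the scheduled Day 1 of each cycle".

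Four sets of by-visit summaries depend on which visit a value belongs to: laboratory values (SAP 5.6.3, which plans "the change from baseline to each postbaseline visit"), vital signs (5.6.4), ECG (5.6.5) and KPS (5.6.6).

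**The concern.** The SAP takes the Cycle 1 visit window, extends it to all cycles, and presents the result as the protocol's rule. It is not offered as a deliberate narrowing. The SAP says it follows the protocol, names Amendment 07 as the version it analyses, and declares no changes in its Section 7. By contrast, the ±5-day tumor assessment window in SAP 8.1.1 does match Table 7 (footnote t).

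What is at stake is limited. A programmer who applies Section 8.2.1 as written would find that some values taken on days the protocol allows fall inside no window. Section 8.2.1 gives no instruction for them. If they were left out, the by-visit tables would rest on fewer subjects at each visit from Cycle 2 on than the trial actually observed.

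**Working it through.** No sample size, power or alpha figure is involved. The check is a day count.

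**Inputs.** SAP window: ±1 day, all cycles (SAP 8.2.1). Protocol visit window: ±1 day in Cycle 1 and ±3 days from Cycle 2 (Table 7, footnotes b and c). Laboratory allowance: 72 hours, that is 3 days, before the visit (footnotes b, c and m). Cycle length: "All Cycles are 21 Days in Duration" (Table 7). Day 1 is the first dose (SAP 5.6).

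**Share of permitted days covered.**

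- Visits from Cycle 2: ±3 days spans 2×3+1 = 7 days and ±1 day spans 2×1+1 = 3. The SAP covers 3 of 7. The days left out are −3, −2, +2 and +3.
- Cycle 1 laboratory samples, with 72 hours counted from the scheduled day: days −3 to +1, which is 5 days. The SAP covers 3 of 5. The days left out are −3 and −2.

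**Target days.** Day d of cycle k is study day 21×(k−1)+d, so C1D15 = 15, C2D1 = 22, C2D15 = 36 and C3D1 = 43.

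| Visit | SAP window | Protocol visit window | Laboratory, 72 h before scheduled day | Laboratory, 72 h before actual visit |
|---|---|---|---|---|
| C1D15 | 14–16 | 14–16 | 12–16 | 11–16 |
| C2D1 | 21–23 | 19–25 | 19–25 | 16–25 |
| C2D15 | 35–37 | 33–39 | 33–39 | 30–39 |
| C3D1 | 42–44 | 40–46 | 40–46 | 37–46 |

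The last two columns differ because Table 7 can be read in two ways. Footnotes b and c count the 72 hours from the scheduled visit. Footnote m says only the visit, which could mean the actual one. In that case the lower limit is the earliest permitted visit day minus 3: 14−3 = 11, 19−3 = 16, 33−3 = 30 and 40−3 = 37.

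- Counted from the scheduled day, these windows do not overlap: 16 < 19, 25 < 33 and 39 < 40.
- Counted from the actual visit, day 16 belongs to both C1D15 and C2D1, and days 37–39 belong to both C2D15 and C3D1.

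Under either reading some days lie in no window, for example days 17–18 under the first and days 26–29 under both. A date-window rule therefore needs a further rule for values in two windows or in none.

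**Number of values affected.** This cannot be computed, because the documents give no distribution of actual visit or sampling dates. It is zero if every visit and sample fell within ±1 day.

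**The case against.** The SAP sentence closely paraphrases footnote b, which does give ±1 day for Cycle 1 visits. The 72-hour allowance is permissive. For Cycle 1 laboratory samples, then, the SAP statement is incomplete rather than wrong. That stands, and it would overstate the point to call the attribution wrong for laboratory samples in every cycle. From Cycle 2 on the attribution is wrong.

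A reader might infer that the SAP discards protocol-compliant safety data. The documents do not support that. Section 8.2.1 never says that a value outside the window is excluded. Its working rule is to choose the closest of several values, and SAP Section 9 leaves the derivation rules to separate documents. Those may already assign values by recorded visit. If so, the tables would be sound and only the SAP text would need correcting.

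A reader might also cite the ±3-day window in the Extension Phase schedule (Table 8). It adds nothing here, because this SAP covers the Randomization Phase (Section 3) and leaves any Extension Phase analysis to a separate plan (Section 5.9).

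None of this removes the mismatch with footnote c, or fills the gap on where a value outside ±1 day should go.

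**Conclusion.** Wrong as written, and minor. The rule in SAP 8.2.1 and the source given for it do not agree with Table 7 from Cycle 2 onward, and they omit the laboratory allowance in Cycle 1. On a literal reading, two groups of values comply with the protocol but have no visit in the by-visit laboratory, vital-sign, ECG and KPS summaries: values from Cycle 2 on taken 2 or 3 days from the target day, and Cycle 1 laboratory samples taken 2 or 3 days early.

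Confidence is high for the text mismatch. For any loss of values the point is conditional on how the window is programmed. The day counts assume target days run from the first dose in fixed 21-day cycles. Analyses that use all observations, including worst-grade laboratory results, are unaffected, as are all hypothesis tests and efficacy endpoints.

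**What to change.** In SAP 8.2.1:

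1. Replace the uniform ±1-day window with the Table 7 windows for all by-visit safety summaries: ±1 day in Cycle 1 and ±3 days from Cycle 2, with laboratory samples accepted up to 72 hours before the visit.
2. Assign any value that falls in two windows, or in none, to its recorded nominal visit or, if there is none, to the nearest target day. The fallback is needed because central laboratory results are the primary source (SAP 5.6.3), and the protocol lists the sampling date as recorded on the CRF (Section 11.5) without mentioning a visit label.
3. Keep the existing closest-observation and tie rules.
4. Limit the clause attributing ±1 day to the protocol to Cycle 1 visits.

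The cost is one or two SAP sentences and a small change to the visit-assignment programming. No visit schedule, sampling time or treatment rule changes.
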